#### 6.4 Primary variable

There are two primary variables:

1. LCIG monotherapy 1 (yes, no) at LCIG initiation and at 3, 6, 9, and 12 months after LCIG initiation

with the following definition:

- LCIG monotherapy means that the patient is not on any add-on PD medication or PD therapy at the respective time point.
- 2. LCIG monotherapy 2 (yes, no) at LCIG initiation and at 3, 6, 9, and 12 months after LCIG initiation

with the following definition:

LCIG monotherapy means that the patient is allowed to take an add-on PD medication or PD therapy at the respective time point, however, only in the evening after the LCIG infusion is completed (i.e. reason for start of add-on PD medication: other).

Additional specifications for both variables are:

- Medications for indications secondary to PD are allowed.
- If the reason for add-on PD medication is missing the medication will be considered as taken during LCIG infusion (i.e. no monotherapy).
- LCIG initiation date is the start date of the first LCIG infusion.
- 3 months after LCIG initiation is calculated as LCIG initiation date + rounded (3 [months] x 30.4 [days]). 6, 9, and 12 months after LCIG initiation will be calculated analogously.
- For LCIG initiation date with missing day the 15th will be used.

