Interim outcomes of the GREENFIELD observational study on 145 patients with APD in Italy compared clinical data before and during LCIG therapy. Initiation of LCIG led to significant clinical improvement and the intake of add-on PD medication was largely reduced: for instance, oral levodopa use decreased from 96.9% before LCIG start to 5% (during the day) and 26% (at night); use of dopamine agonists decreased from 64.1% to 30%. However, thus far, results are only derived from a mean treatment period of 14 months, and date are still incomplete [9].

Rationale

LCIG (Duodopa®) appears to possess the potential to be used as monotherapy in many patients, or at least enable significant reductions of the add-on PD medication. Thereby, LCIG may achieve a much-needed simplification of the treatment regimen, allowing for a reduction of detrimental drug-drug interactions [6].

So far, data on patients in whom LCIG monotherapy or significant reductions of add-on PD medication was achieved, have been derived from two clinical studies with rigorous protocols [7, 8], and therefore cannot be easily translated into routine clinical practice. Also, recent observational studies demonstrated overall varying approaches in the management of add-on PD medications in routine clinical practice before and after initiation of LCIG treatment [9, 10].

For APD patients under LCIG treatment there is an opportunity to substantially reduce the need for other add-on PD medication and/or completely discontinue them. This is the primary hypothesis that generates this study.

In summary, no systematic, comprehensive and homogeneous real-world data are available – neither on LCIG monotherapy or LCIG in combination with add-on PD medication, nor on the management (reasons for use and time course) of add-on PD medications before or upon LCIG initiation, or during long-term LCIG maintenance therapy.

The present study attempts to fill this knowledge gap and generate relevant data from routine clinical practice on the usability of LCIG as a monotherapy and in combination with add-on PD medications. In addition, useful data on the handling of add-on PD medication (e.g., tapering, introduction), upon LCIG initiation and over long-term use shall be collected.

Research Question and Objectives 8.0

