9.2.7.5 Previous PD medication and add-on PD treatment during **LCIG Treatment**

Data on previous PD medication (right before initiation of LCIG treatment) will include date of drug initiation and/discontinuation, reason for its discontinuation, drug name, total dose per day, posology, and attempts of previous device-aided therapies (e.g., CSAI, DBS).

Data on add-on PD medication upon LCIG initiation or during LCIG treatment will include date of drug initiation/discontinuation, drug name, total dose per day, posology, tapering* process (duration and posology), starting and end date of LCIG titration, reasons for add-on drug therapy (severity and frequency), timing of add-on drug (during/outside of infusion hours).

Levodopa equivalent daily dose (LEDD) table published by Tomlinson, et al will be used to calculate LEDD. [47]. Each PD medication amount should be multiplied by the appropriate value to obtain the corresponding LEDD. Adding together the corresponding LEDD for each PD medication, will be providing the total LEDD.

9.2.7.6 **Concomitant Disease and Medication**

Information on concomitant disease and medication (non-PD treatment) will be collected and reported in the eCRF, including drug name, indication, start/stop date, and dosages.

^{*}The term "tapering" is used within this study in the context of drug treatment. It refers to the process of reducing a certain drug dosage incrementally (over a few days or weeks), instead of its abrupt discontinuation. For some PD medications a tapering process is needed to avoid a withdrawal syndrome

9.2.7.7 **LCIG Treatment**

Information on LCIG treatment from initiation until the day of the visit will be documented in the eCRF, including reason(s) for initiation of LCIG treatment, date of introduction of LCIG, use of nasojejunal tube, date of PEG-J procedure, date of titration and duration of titration process, infusion settings (infusion time, morning dose, continuous infusion rate, total daily dose) and dose modification (number of dosage changes, new infusion settings or temporary interruptions in LCIG daily infusion rate and reasons for dosage adjustment).

A LCIG substantial dose adjustment is defined as any increase or decrease of the total daily LCIG dose by more than 20% of total daily dose.

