LCIG monotherapy is defined as being treated with LCIG as the only PD medication that the patient is taking during the LCIG infusion hours. LCIG long term monotherapy is defined as a time period of at least 12 months of continuous LCIG monotherapy.

9.2.7.8 **Current APD Status at study visit**

Parkinson's disease status will be measured by the physician using the following scales: mentation/behaviour/mood (UPDRS I), activities of daily living (UPDRS II), motor examination (UPDRS III), complications of therapy (UPDRS IV) and Modified Hoehn and Yahr Stage (UPDRS V), non-motor symptoms (NMSS) will be recorded and Mini-Mental State Examination (MMSE).

The patient will be requested to fill in the following questionnaires:

- Questionnaire for Impulsive-Compulsive Disorder in Parkinson's Disease- Rating Scale (QUIP-RS)
- Parkinson's disease Sleep Scale Version 2 (PDSS-2).

9.2.7.9 **Healthcare Resource Utilization**

The HCRU Questionnaire will contain questions on the occupational status, nursing home visits, hospitalizations, emergency care visits, caregiver support, including the patient's opinion on PD medication as retrieved by the following questionnaires, which the patient will be requested to complete:

Beliefs Medication Questionnaire (BMQ)

In addition, the patient/caregiver will be requested to state their overall preference on LCIG as a monotherapy vs. LCIG plus add-on PD medication.

Quality of Life 9.2.7.10

In order to assess the patient's quality of life, the patient will be asked to complete the Parkinson's disease Quality of Life Questionnaire (PDQ-8).

Table 1 Summary of assessments

Observation	Before LCIG initiation	LCIG initiation	During LCIG treatment	Patient visit
2	Retrospect	ive Data from Patie		
Center Characterization	X			
Physician experience and treatment preference	X			
Patient demographics	X			
Patient socio- demographics	X			X
Medical History and PD History	X			X
PD medication before starting LCIG	X			
Reason(s) for LCIG initiation		Х		
LCIG infusion data		X	х	X
Add-on PD medication since LCIG initiation		X	X	X
Concomitant Medication (non-PD treatment)	х	X		X
Behaviour/mentation/mood (UPDRS Part I)				X
Activities of daily living (UPDRS Part II)				X
Motor examination (UPDRS Part III)				X
Treatment complications (UPDRS Part IV)				X
Disease Stage (ModifiedHoehn & Yahr stage, UPDRS Part V)	x			х
Non-motor Symptoms Scale (NMSS)				X
Questionnaire for Impulsive-Compulsive Rating Scale (QUIP-RS)				X

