## 1 Study protocol and scope

This statistical analysis plan (SAP) describes the final analysis of "COSMOS". It is based on the final version of the protocol (no. P16-831), dated 14 June 2017, and on Administrative change no. 1, dated 02 November 2017.

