#### Motor symptoms

Separately for 'immediately prior to LCIG initiation' and 'visit':

- Number of motor symptoms
- Number of motor symptoms in appropriate categories
- Bradykinesia (yes, no, unknown)
  - If yes: Severity

Frequency

- Rigidity (yes, no, unknown)
  - o If yes: Severity

Frequency

- Tremor (yes, no, unknown)
  - o If yes: Severity

Frequency

- Dystonia / cramps (yes, no, unknown)
  - o If yes: Severity

Frequency

- Gait Impairment (except freezing of gait (FOG); yes, no, unknown)
  - If yes: Severity

Frequency

- Balance problems (yes, no, unknown)
  - o If yes: Severity

Frequency

- Hypophonia (yes, no, unknown)
  - o If yes: Severity

Frequency

- Dysphagia (yes, no, unknown)
  - o If yes: Severity

Frequency

- Nocturnal/morning akinesia (yes, no, unknown)
  - If yes: Severity

Frequency

- Freezing of gait (FOG; yes, no, unknown)
  - If yes: Severity

Frequency

- Other (yes, no)
  - If yes: List of symptoms

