#### Reasons:

- For each add-on PD medication/therapy at the time points LCIG initiation and at 3, 6, 9, and 12 months after LCIG initiation and at visit::
  - Reason for start (multiple answers)
  - If not ongoing: reason for discontinuation (multiple answers)
- Reason for change on LCIG dose in general
- Reason for LCIG dose changes (multiple answers) by 5%, 10%, 15%, 20% or 25% or higher
- Reason for substantial LCIG dose changes (multiple answers) with substantial change defined as any increase or decrease of the total daily LCIG dose by more than 20%
- Latency and duration of treatments:
  - For patients with add-on PD medication or PD therapy at LCIG initiation: Time from LCIG initiation until LCIG is given as a monotherapy (separately for monotherapy 1 and monotherapy 2 definition)

[figure not shown]
Only patients with add-on PD medication or PD therapy at LCIG initiation

 For patients with add-on PD medication or PD therapy at LCIG initiation and separately for patients with and without ongoing monotherapy at visit: Duration of LCIG monotherapy (separately for monotherapy 1 and monotherapy 2 definition) Only patients with add-on PD medication or PD therapy at LCIG initiation Analysis a) Without ongoing monotherapy until visit

Analysis b) With ongoing monotherapy until visit

- For each add-on PD medication/therapy:
   Time from LCIG initiation until the respective add-on PD medication/therapy is started or changed
- Time from LCIG initiation until the first LCIG dose change by 5%, 10%, 15%, 20% or 25%
- Time from LCIG initiation until the first substantial LCIG dose change with substantial change defined as any increase or decrease of the total daily LCIG dose by more than 20% in relation to first LCIG infusion
- LCIG monotherapy (1 and 2) vs. LCIG plus add-on PD medication:
  - o HCRU:
    - Primary occupation (retired, on sick leave, unemployed, working full time, working part-time, student)
      - If retired: due to PD (yes, no)
      - If on sick leave: due to PD (yes, no)
      - If unemployed: due to PD (yes, no)
    - Permanent living in a nursing home/institution (yes, no)
    - Help in daily activities
    - Frequency of visits:
      - General practitioner

- Nurse
- Occupational/speech therapist
- Physiotherapist
- Psychologist and/or psychiatrist
- Dietician
- Discussion of LCIG monotherapy (yes, no, patient did not remember)
- Offering of LCIG monotherapy (yes, no, patient did not remember)

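### SAP 6.4 sets monotherapy 2 by reason for start 'other' and evening use, not by the planned during/outside-infusion timing item, so it can depart from the protocol definition; the first time point also has two different anchors

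*SAP*

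**What the plan says.** **Definition.** Protocol 9.2.7.7: "LCIG monotherapy is defined as being treated with LCIG as the only PD medication that the patient is taking during the LCIG infusion hours". The criterion is timing.

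**Planned data.** Protocol 9.2.7.5 lists, for each add-on drug, "reasons for add-on drug therapy (severity and frequency), timing of add-on drug (during/outside of infusion hours"). Reasons and timing are separate items.

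**SAP rule.** SAP 6.4 has two primary variables. Monotherapy 1 requires no add-on at all. Monotherapy 2 permits an add-on "only in the evening after the LCIG infusion is completed (i.e. reason for start of add-on PD medication: other"). A companion rule reads: "If the reason for add-on PD medication is missing the medication will be considered as taken during LCIG infusion (i.e. no monotherapy"). In SAP 6.5 the reason field is "Reason for start (multiple answers"). The SAP variable lists do not include the timing item.

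**First time point.** The protocol abstract (4.0) places it after permanent system placement. Protocol 8.0, 9.1 and 9.5 name no event. SAP 6.4 uses the start of the first LCIG infusion.

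**Link between the documents.** SAP 1 rests on the protocol "and on Administrative change no. 1, dated 02 November 2017". SAP 2.5 states that the SAP agrees with the protocol and that substantial deviations are described. Neither difference above is described.

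**The concern.** Monotherapy 2 is the primary variable closest to the protocol definition, because monotherapy 1 is stricter. If a residual reason category stands in for time of intake, the reported percentage may answer a different question from the one the protocol poses. The same classification carries into the 12-month comparison groups (SAP 7.4 and 7.6), the latency and duration summaries (SAP 6.5) and the regression with monotherapy 2 as response (SAP 7.8). The confidence interval reflects sampling error only.

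The anchor matters for the 'at initiation' percentage. Protocol 7.0 describes an optional nasojejunal test phase before the permanent tube, and says that other therapies are usually tapered over a titration period. A percentage taken at the first infusion can therefore describe patients who are still tapering.

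**Working it through.** **1. The plan's own figure.** Protocol 9.5 asks for a half-width of 5 points at p = 50% with two-sided 95% confidence: n = 1.96² × 0.5 × 0.5 / 0.05² = 384.16, rounded up to 385. It reproduces and is not in dispute. It says nothing about classification.

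**2. The two definitions side by side, for a patient with one add-on drug.**

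| Add-on drug | Protocol 9.2.7.7 | SAP 6.4, monotherapy 2 |
|---|---|---|
| Evening only, reason 'other' alone | yes | yes |
| During infusion, specific reason | no | no |
| Before the morning start of infusion | yes | no by the prose; by the code it depends on the reason |
| Evening only, 'other' plus another reason | yes | not stated |
| Outside infusion hours, reason missing | yes | no |
| Evening only, specific reason | yes | yes by the prose, no by the code |
| During infusion, reason 'other' | no | no by the prose, yes by the code |

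The third and fourth rows follow from the text alone. The fifth is a rule stated in advance that can only lower monotherapy 2. The last two arise only if 'other' on the final form does not itself mean evening use, which the documents do not settle.

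**3. What limits the error.** Let T be the patients who meet the protocol definition. A patient with no add-on belongs to monotherapy 1, to monotherapy 2 and to T.
- A false 'yes' is in monotherapy 2 but not in T, so it is not in monotherapy 1. At each time point, the share of false 'yes' is at most (monotherapy 2 %) − (monotherapy 1 %). Both percentages are reported.
- A false 'no' is in T but not in monotherapy 2. The gap does not limit it; the only ceiling is 100% − (monotherapy 2 %).

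**4. Anchor.** The abstract's event is permanent placement and the SAP's is the first infusion. They differ for a patient whose first infusion was in the nasojejunal phase. Tapering may then be incomplete, so the SAP percentage at initiation may be lower than the one the abstract describes. SAP 6.3 records whether a test phase took place, but the documents give no number of patients.

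**5. Later time points.** SAP 6.4 gives 3 × 30.4 = 91.2, 6 × 30.4 = 182.4, 9 × 30.4 = 273.6 and 12 × 30.4 = 364.8, that is days 91, 182, 274 and 365 from first infusion. Eligibility (Protocol 9.2.4) guarantees only 12 months on LCIG. Starting this clock at a later placement date could put the 12-month point after the visit.

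**The case against.** The strongest reply is that the final form may carry timing inside the reason field. SAP 6.4 equates evening use with 'other', and treating a missing reason as intake during infusion makes most sense if that field encodes timing. Protocol 9.2.7.5 lists planned items and is not the form. The data capture system also differs between protocol 9.6 and SAP 2.1, and Administrative change no. 1 lies in between. This stands, and it rules out saying that patients *are* misclassified. It does not remove the point: the SAP never says what 'other' codes, the evening wording is narrower than the protocol's, and combined reasons have no rule.

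The reply is also right that the SAP already gives some protection: monotherapy 1 is reported alongside, and SAP 6.5 tabulates reasons for start.

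Several stronger readings are tempting but unsupported:
- *Sizing the error from the observational study in Protocol 7.0*, where "oral levodopa use decreased from 96.9% before LCIG start to 5% (during the day) and 26% (at night"). Those are interim data from another cohort and the split covers oral levodopa only. False 'yes' errors would arise among daytime users, whom the night share does not represent.
- *A drug for nocturnal or morning akinesia must count against monotherapy 2.* SAP 6.3 lists "Nocturnal/morning akinesia (yes, no, unknown") as a symptom. No passage lists the reason options.
- *Add-ons under 24-hour infusion, or surgical therapies, become evening use.* That needs the code to be applied while ignoring the sentence it explains; read literally, the prose excludes them.

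On the anchor, it is fair to say that the placement wording appears only in the abstract and that the SAP date is explicit and usable. What remains is that two stated events differ for the same primary endpoint.

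**Conclusion.** The concern holds as a mismatch between the documents. The SAP rule for monotherapy 2 can depart from the protocol definition because it replaces the planned timing item with a reason code, restricts permitted use to the evening, and leaves combined reasons undefined. Separately, the first time point is tied to different events in the abstract and the SAP, and the percentage at initiation may be lower than the one the abstract describes.

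No magnitude is claimed: neither the size nor the direction of any net error in monotherapy 2 can be computed from the documents. Over-counting is limited by the gap between the two reported percentages, provided that both are computed in the same patients; under-counting is not. A reader might infer that the primary result is wrong, but the documents do not show that.

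Confidence is high for the mismatch and moderate for any effect on results. It should be fixed, because the change is cheap and concerns a primary variable.

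**What to change.** In SAP 6.4:
- Derive monotherapy 2 from the during/outside-infusion timing item where it was collected. Use reason for start only where timing is missing or was not collected.
- State what 'other' codes on the final form.
- Report monotherapy 2 with 'other plus another reason' counted both ways.
- If timing was not collected at all, limit the sensitivity analysis to the combined-reason and missing-reason groups. Reclassifying every add-on would be uninformative: all 'during' essentially returns monotherapy 1, and all 'outside' gives about 100%.

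For the first time point, reconcile the protocol abstract with SAP 6.4. If the PEG-J date planned in Protocol 9.2.7.7 was collected, report the first percentage at both dates. Keep the 3, 6, 9 and 12-month clock from first infusion. If the date was not collected (SAP 6.3 lists only hospitalization for placement), only the wording can be reconciled.

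Describe both departures as SAP 2.5 requires, unless Administrative change no. 1 already covers them.

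Cost: SAP wording, some programming and one or two extra percentages. No new patients or procedures are needed.

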#### 6.5 Secondary variables

#### Descriptive data from patient's PD medication

Add-on PD medication:

At the time points LCIG initiation and at 3, 6, 9, and 12 months after LCIG initiation, at visit and at appropriate time points between 12 months after LCIG initiation and the visit:

 Add-on PD medication (multiple answers; category and medication/therapy; patient based)

Category and medication/therapy are as follows:

Category	Medication/therapy
Levodopa	Levodopa/carbidopa Levodopa/benserazide Levodopa/carbidopa/entacapone Other
COMT inhibitor	Entacapone Tolcapone Opicapone Other
Dopamine Agonist (excluding Apomorphine)	Pramipexole Ropinirole Cabergoline Rotigotine Other
MAO Inhibitor	Selegiline Safinamide Rasagiline Other
NMDA Antagonist	Budipine Amantadine Other
Apomorphine	Apomorphine intermittent injection SC Apomorphine subcutaneous continuous infusion 30mg/ml solution Other
Anticholinergics	Anticholinergics Other

Surgical therapy	Pallidotomy Thalamotomy Deep brain stimulation (DBS) Stem Cell Transplant Other
Other	-

- Total daily dose separately for each category and for each medication/therapy (except all 'Other', Anticholinergics, and Surgical therapy; Apomorphine only if possible)
- Levodopa equivalent daily dose (LEDD) separately for each category and for each medication/therapy if applicable (see Section 7.6)
- Total daily LEDD (in mg; see Section 7.6)
- Posology (i.e. average number of intakes per day) separately for each category and for each medication/therapy (except all 'Other' and Surgical therapy)
- Add-on PD medication in categories and medication/therapy (multiple answers)

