To assess the generalizability of the data from the patients enrolled, the physician will be asked to document on a separate Case Reporting Form the number of patients who are eligible but refuse to participate in the study. Only age ranges (<30 years, 30-45 years, 45-65 and > 65 years) and reason(s) for not participating will be collected.

The primary endpoint of this PMOS will be the percentages of APD patients on LCIG monotherapy right after LCIG initiation and at 3, 6, 9, and 12, respectively.

The secondary endpoints are:

- Descriptive data from patient's PD medication:
 - For add-on PD medication: percentage of patient on each PD medication (by drugs and class), total daily dose and levodopa equivalent Daily dose (LEDD), posology (number of times per day);
 - For LCIG infusion settings and substantial dose adjustments: total dose per day and specific for each type of dose (morning dose and continuous dose) and number of hours of infusion.

- Tapering process: number of days required for the tapering process, total dose per day and posology for add-on PD medication prior to LCIG initiation, at LCIG initiation (titration) or during ongoing LCIG treatment
- Main reasons for introduction or tapering of add-on PD medication or LCIG substantial dose adjustments
- Latency and duration of treatments data:
 - Number of days or months from LCIG initiation until LCIG is given as a monotherapy and the duration of LCIG monotherapy.
 - Number of days or months from LCIG initiation until the introduction or tapering of each PD medication, or until any LCIG substantial dose adjustments.
- LCIG monotherapy vs LCIG plus add-on PD medication data:
 - Healthcare Resource Utilization, as measured by Healthcare Resource Utilization Questionnaire (HCRU)
 - Patient's, caregiver's, and physician's overall preference on LCIG monotherapy vs. LCIG plus add-on PD medication, percentage of patient's and physician's preference for each of the options
 - Predictors for LCIG as monotherapy vs. LCIG plus add-on PD medication based on the patient's profile, including socio-demographics, clinical status (motor and non-motor symptoms), Levodopa-equivalent dose (LED), PD medication and Quality of Life
 - Predictors for LCIG as monotherapy vs. LCIG plus add-on PD medications based on the physician's profile including experience as measured by number of years on APD patient management, number of years using LCIG therapy, and number of patients on LCIG therapy

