## 3.2 Secondary objectives

The secondary objectives of this study are:

- To describe PD medication management, and the main reasons justifying their use, directly prior to LCIG initiation, at LCIG initiation and during long-term LCIG treatment
- To describe LCIG infusion settings and substantial dose adjustments and the respective reasons
- To describe the Healthcare Resource Utilization (HCRU)
- To identify the physician's and patient's/caregiver's overall preference for the pharmacological treatment approach using LCIG as monotherapy vs. LCIG plus add-on PD medication
- To identify predictors for achieving long-term monotherapy with LCIG vs. LCIG plus add-on PD medication, based on the patient's profile and the physician's profile
- To describe the latency from LCIG initiation until LCIG is given as a monotherapy and the average duration of LCIG monotherapy
- To describe the latency from the initiation of LCIG therapy until the introduction or tapering of each PD medication, or until substantial dose adjustments of LCIG
- To evaluate the percentage of patients who are on LCIG monotherapy, PD medication management and HCRU for the participating countries who have enrolled a minimum of 20 study subjects

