#### 4.4 Methods of measurement and documentation

Patient data and site characteristics were to be documented on the eDRF. In addition, patients were asked to complete the following questionnaires: Parkinson's Disease Quality of Life Questionnaire (PDQ-8), Questionnaire for Impulsive-Compulsive Disorders in Parkinson's Disease - Rating Scale (QUIP-RS), Parkinson's Disease Sleep Scale-2 (PDSS-2), and Beliefs Medication Questionnaire (18-item BMQ). Physicians should complete the following questionnaires: Unified Parkinson's Disease Rating Scale (UPDRS), Non-Motor Symptoms Scale for Parkinson's Disease (NMSS), Mini-Mental State Examination (MMSE), and Healthcare Resource Utilization Questions (HCRU). Data from questionnaires were also to be recorded on the eDRF.

An overview of activities and procedures is given in Table 4-1.

Table 4-1: Activities and procedures

Activity/Procedure	Before LCIG initiation	LCIG initiation	During LCIG treatment	Patient visit
	Retrospective data from patient files			
Center characteristics	X			3
Physician experience and treatment preference	X			
Patient demographics	X		ė.	
Patient socio-demographics	X			X
Medical History and PD History	X			X
PD medication before starting LCIG	X			
Add-on PD medication since LCIG initiation		X	X	X
Clinical PD status	X	X		
LCIG infusion data		X	X	X
Concomitant Medication (for indications secondary to PD)	X	X	X	X
Behaviour/mentation/mood (UPDRS Part I)	X		2	X
Activities of daily living (UPDRS Part II)	X			X
Motor examination (UPDRS Part III)	X			X
Treatment complications (UPDRS Part IV)	X			X
Disease Stage (Modified Hoehn & Yahr stage, UPDRS Part V)	X			X
Non-motor Symptoms Scale (NMSS)				X
Questionnaire for Impulsive-Compulsive Rating Scale (QUIP-RS)			6	X
Mini-Mental State Examination (MMSE)	X			X
Quality of Life (PDQ-8)			ā	X
Parkinson's disease Sleep Scale Version 2 (PDSS-2)				X
Healthcare Resource Utilization Questions (HCRU)				X
Beliefs Medication (BMQ)				X
Adverse Events / Adverse Reactions / Product complaint		X	X	X

In detail the following information was documented:

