#### Historical therapy discontinued prior to considering LCIG initiation

- Any device aided therapy other than LCIG in the past (yes, no)
  - If yes: Therapy (multiple answers)

Separately for DBS and Apomorphine:

- Duration: over all entries the treatment duration (end date minus start date +1) will be summarized
- Reason for discontinuation (multiple answers)
- Any dopamine agonists in the past (yes, no)
  - o If yes: Therapy (multiple answers, patient based)

Separately for each therapy:

- Duration: over all entries the treatment duration (end date minus start date +1) will be summarized
- Reason for discontinuation (multiple answers)

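### PD medication just before LCIG is collected and named in the first secondary objective, but SAP 6.5 plans no output for it, so any reduction made before the first infusion cannot be seen

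*SAP*

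**What the plan says.** **Promised.** SAP 3.2, like Protocol 8.0, sets out to describe PD medication management "directly prior to LCIG initiation, at LCIG initiation and during long-term LCIG treatment". The tapering endpoint in Protocol 9.1 also asks for "total dose per day and posology for add-on PD medication prior to LCIG initiation, at LCIG initiation (titration") and during ongoing treatment. Protocol 7.0 (Rationale) says that LCIG offers an opportunity to cut add-on medication substantially or stop it altogether, and adds: "This is the primary hypothesis that generates this study".

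**Collected.** Protocol 9.2.7.5: "Data on previous PD medication (right before initiation of LCIG treatment) will include" drug name, total daily dose, posology and dates. Protocol Table 1 and SAP Table 4-1 both carry a row "PD medication before starting LCIG", marked in the column for the period before initiation.

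**Analysed.** SAP 6.5 reports add-on PD medication (drug and category, total daily dose, LEDD, posology) "At the time points LCIG initiation and at 3, 6, 9, and 12 months after LCIG initiation, at visit and at appropriate time points" between month 12 and the visit. SAP 6.4 fixes the earliest of these: "LCIG initiation date is the start date of the first LCIG infusion".

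**The concern.** An objective with three phases has planned tables for only two. The missing phase is the regimen patients were on when the decision for LCIG was made. Without it the report cannot say what patients came from.

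It looks like an oversight rather than a decision. The SAP reports motor symptoms, non-motor symptoms, treatment-related symptoms and co-morbidities (6.3) immediately prior to LCIG and at the visit. It does the same for UPDRS and, where available, MMSE, and it computes a change from before LCIG to the visit for OFF time and dyskinesia (7.4). Medication, the subject of the study, has no equivalent. SAP 2.5 states that the plan agrees with the protocol and that substantial deviations are described; none is described here.

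At stake is the reduction half of the stated hypothesis. Drugs stopped or lowered between the decision for LCIG and the first infusion would appear in no planned comparison. Protocol 7.0 reports that one of the two cited clinical trials required tapering before LCIG initiation, so this interval is not hypothetical.

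**Working it through.** No alpha, power or sample-size figure bears on this point, and the required 385 evaluable patients are unaffected. The check has two parts.

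**1. Does any other SAP item supply the pre-LCIG regimen?**

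| SAP item | What it gives | Fills the gap? |
|---|---|---|
| 6.3, "Historical therapy discontinued prior to considering LCIG initiation" | Past device-aided therapies and dopamine agonists already stopped; duration and reason only | No: no dose or LEDD, and no levodopa, COMT inhibitors, MAO inhibitors or amantadine |
| 6.3, lists headed before LCIG initiation | Medication for indications secondary to PD | No: not PD medication |
| 6.5, tapering, minimum and maximum dose | Extremes per drug over all treatment phases, a term left undefined | Possibly in part; extremes are not the regimen just before LCIG |
| 6.5, tapering, dose and posology by time point | Starts at initiation | No |
| 7.6, differences | LCIG total daily dose only | No: none for add-on medication or LEDD |
| Table 7-2, LEDD as predictor | Value at initiation | No |

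**2. How much could a reader miss by using initiation as the starting point?**

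Let P be the percentage on any add-on PD medication just before LCIG, f the share of those patients who stop all of it before the first infusion, and E the percentage on add-on medication at month 12. For simplicity, nobody starts an add-on before the first infusion.

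- Fall from before LCIG: P − E
- Fall seen from initiation: P × (1 − f) − E
- Hidden part: P × f, whatever E is

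No value for this study is given, so P, f and E are assumptions. The ranges for P and E borrow from Protocol 7.0: 89% and 80% on add-on medication in the two cited trials; E = 60% as the complement of the upper 40% on monotherapy in the multinational registry; E = 23% as the complement of 77% on monotherapy at week 54 of the open-label trial.

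| P | E | Fall from before LCIG | Seen, f = 0 | Seen, f = 25% | Seen, f = 50% |
|---|---|---|---|---|---|
| 89% | 60% | 29.0 | 29.0 | 6.8 | −15.5 |
| 89% | 23% | 66.0 | 66.0 | 43.8 | 21.5 |
| 80% | 60% | 20.0 | 20.0 | 0.0 | −20.0 |
| 80% | 23% | 57.0 | 57.0 | 37.0 | 17.0 |

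Entries are percentage points; a negative value is an apparent rise. Example: 89 × 0.75 − 60 = 6.75. For P = 89% the hidden part is 89 × 0.25 = 22.25 or 89 × 0.50 = 44.5 points.

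Two published contrasts in Protocol 7.0 do not settle f. The fall from 89% to 37% by day 1 of the extension study follows a double-blind phase in which prior medication had to be kept and one arm already received LCIG, so it does not isolate tapering before a first infusion. The fall in oral levodopa from 96.9% to 5% by day and 26% at night comes from interim results of an Italian observational study that the protocol itself calls incomplete, and it does not say when the drugs were stopped.

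**The case against.** The best defence is that initiation is a serviceable starting point. It is the first infusion, and Protocol 7.0 describes other therapies being tapered during a titration period; SAP 6.5 defines a subgroup still on add-on medication at initiation. If little is stopped earlier, f is near zero and almost the whole fall is visible. This stands as a limit on the size of the problem. It does not supply the missing phase, and nobody can confirm that f is small without tabulating the pre-LCIG regimen.

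Second, SAP 6.5 plans no change in add-on medication from initiation either, so there is no estimate to be biased. That is correct: this is an omission. The table above shows what a reader would compute from the planned outputs.

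Third, the tapering section may already reach back before LCIG. Its phases are undefined and its figures are not reproduced in the available text, so partial coverage cannot be excluded. Even then it gives minimum and maximum doses per drug, not the regimen or LEDD directly before LCIG.

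Fourth, SAP 7.10 allows extensions without constraint. That permits the missing table but does not plan it, and a before/after comparison added once the data are known would be post hoc.

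Finally, the objective is descriptive, so formal inference on change is not owed. Accepted: a confidence interval for the change is optional.

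**Conclusion.** The gap is real and narrow. PD medication directly before LCIG is promised and collected, but SAP 6.5 gives no output for it. One of the three phases of the first secondary objective, and the pre-LCIG dose and posology in the protocol's tapering endpoint, are therefore not reported as planned, subject to what the undefined tapering phases turn out to cover. Any reduction made before the first infusion is invisible. Its size is P × f, from nothing up to 44.5 points over the assumed ranges; the true value for this study is unknown.

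A reader might infer that the objective and the hypothesis have no baseline at all, or that the plan could never show a large fall in add-on medication. The documents do not support either. The initiation and long-term phases are covered, change from the first infusion onward can be read from the SAP 6.5 tables, and complete discontinuation is measured by the two monotherapy variables, which need no pre-LCIG value. The primary endpoint and the sample size are untouched. The omission should be corrected, but it does not threaten the study's main result.

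**What to change.** 1. In SAP 6.5, add the time directly before LCIG initiation as the first time point for the percentage on each drug and class, total daily dose, LEDD and posology.
2. In SAP 7.6, add a descriptive within-patient change in total add-on LEDD and in number of PD drugs, from that time point to initiation, month 12 and the visit. A 95% confidence interval is optional. Label the LEDD as add-on only, since Table 7-1 has no row for LCIG.
3. In the tapering part of SAP 6.5, define the treatment phases and state whether they include the period before LCIG.

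The cost is one column per table, one simple paired summary and one sentence of definition. No new data and no change in sample size are needed.
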